6. STATISTICAL METHODS

We plan to use descriptive statistics to summarize baseline patient and physician-level variables both overall and by arm. We will use mean±standard deviation (or median and interquartile range [IQR] as appropriate) for continuous variables and frequency / percentage for categorical variables. Specifically, we will summarize age, sex, Keele STarT score, baseline patient-reported outcome scores (PROMIS-PI and ODI), analgesic medication prescription at ED discharge, and the variables listed above. Analyses will involve normal theory methods in general, and in cases of violations of assumptions, we will consider transformation and / or nonparametric / exact methods as appropriate.

Analyses will assume a two-sided 5% significance level. All primary efficacy and safety analyses will be pre-specified as outlined in this SAP, and deviations from planned analyses or post hoc analyses will be labeled as such in any reports or dissemination materials. We do not plan to control for multiple hypothesis tests.

In analyses for each outcome, we plan to control for the respective outcome value at baseline (i.e., in an analysis of covariance [ANCOVA] approach). Analyses for the primary outcome (Y) will involve a linear mixed model (LMM) with repeated measures with fixed effects for: study arm, baseline outcome score (Y0), timepoint, timepoint-by-arm interaction, and known influential predictor effects (age, sex, Keele STarT score). Inference will focus on treatment impacts for the outcome at three months. We will include a random physician effect to account for both within and between physician variability and also to allow for estimation of the intra-cluster correlation coefficient (ICC). The repeated measures on the same participant over time will also introduce a correlation structure across time points, providing the justification for modeling the correlation structure at the

participant level over time. We will use an unstructured correlation matrix to account for the repeated measures within a participant as this has the least assumptions. If the model does not converge or parameters cannot be estimated under this unstructured covariance pattern, we will explore simpler covariance patterns using residual estimated maximum likelihood (REML) comparisons. Including repeated measures per participant will allow us to make most use of all participant data after baseline. We will use assume an unstructured covariance across time.

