In addition to repeating the above analyses with exploratory outcomes, we will conduct exploratory analyses to study effects among subgroups of patients (moderator analyses) and examine the potential impact of PT use among patients in the control arm.

Planned moderator analyses will include the following moderators:

1. Opioid naivete as measured by whether patients report taking opioids within the last 24 hours at their index ED visit or have a history of opioid prescription filling in the Illinois prescription monitoring program within the last 3 months.
2. Initial symptom burden measured as “moderate/severe” if their baseline measures of PROMIS pain scores are ≥ 60 or their STarT score registers as “high risk,” defined as a subscore ≥ 4 (questions 5-9).
3. Age ≥ 65 years old
4. Primary treatment classification, as per the clinical care protocol (directional preference, traction, stabilization, manipulation, nociplastic presentation). As primary treatment classification is assigned only in those participants in the treatment arm (NEED-PT), we will use two approaches to study the effects of treatment classification. First, we will modify GLMM to include treatment classification effects (as opposed to just a study arm effect). Second, we will use matching methods (e.g., propensity score matching or augmented synthetic controls) to match individuals in the NEED-PT arm who have a given primary treatment classification to control arm participants on baseline covariates. We would then use GLMM to estimate the impact of each treatment classification separately.

Analyses will focus on PROMIS-PI scores measured three months after patients’ index visits, as well as ODI scores and opioid use (proportion using an opioid within the last 24 hours) at the same time point. Analyses will involve generalized linear models with appropriate link functions (identity for PROMIS-PI and logit for opioid

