use) that include fixed effects for baseline measures of the outcome of interest, treatment assignment, a moderator variable, and a treatment-moderator interaction. As above, PROMIS-PI will be modeled with standard normality assumptions, which will be evaluated via residual diagnostics and appropriate transformations will be used as necessary. Separate models will be fit for each outcome and moderator. Tests for the treatment-moderator interaction will be two-sided with a 5% type I error rate, and we will report point estimates and 95% confidence intervals. For the logistic regression involving opioid use, we will use Wald confidence intervals and Wald tests. We will not make multiple comparison adjustments.

Mediation analyses will focus on PCS and PSEQ as possible mediators. Our hypotheses are that embedding a PT in the ED can impact patients downstream pain catastrophizing and self-efficacy which will in turn lead to lower reported pain and less frequent opioid use. Our key dependent variables will be PROMIS-PI and opioid use at three months after the index visit. PCS and PSEQ measured at one month will be the mediators of interest. We will use a nonparametric approach to analyses, running separate models for each outcome and mediator (5). In addition, we will examine the possible correlation between mechanisms by using a joint nonparametric estimation framework (6).

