8. POWER AND SAMPLE SIZE CONSIDERATIONS

Power calculations focus on the primary endpoint of PROMIS-PI at three months, and we desire adequate (at least 80%) power to detect the minimum clinically important PROMIS-PI score difference of 3.5-5.5 points as previous literature suggests (8). If we assume a standard deviation of 10 points, which is the defined standard deviation of PROMIS-PI, this corresponds to a desired minimal detectable effect size of $d=0.35$ standard deviation unit difference across arms. Power considerations also account for a 20% drop-out rate for physician clusters (e.g., physician leaves the practice or refuses participation after randomization) and a 20% lost to follow-up rate among recruited participants. We used “The Shiny CRT Calculator” to explore varying assumptions on cluster size (i.e., average number of participants per physician), number of clusters/physicians, and ICC. Under the parallel-arm, “cohort” design, with baseline measurement of primary outcome (PROMIS), the calculator also allows for an assumption on correlation between baseline and follow-up. The table below illustrates power to detect at least a 3.5 mean difference across study arms if we assume just two time points (baseline and three months, which we deem conservative as we will have up to seven time points of observation, including baseline) per participant with a correlation between the two of approximately 0.50. We conservatively estimate that we will need to enroll up to 360 total participants to account for worst-case (20%) scenario dropout for both physicians and participants. **Thus, after accounting for physician and participant dropout, a final sample size of 16 physicians per arm and 7 participants per physician (n=224 total or 112 per arm) achieves 84% power** to detect a mean between-arm difference of 3.5 PROMIS-PI points assuming standard deviation of 10 points, ICC of 0.10, and a two-sided 5% level of significance. In our pilot work, we found a small ICC (0.01-0.04), indicating minimal within-physician effects that were not significant; however, we utilize a more conservative estimate of the ICC at 0.10 in the event that greater than anticipated within-physician effects are encountered. In the event that ICC is lower than expected or dropout rate is lower than 20%, we anticipate often over 90% to detect a meaningful difference across arms. Similar effect size in secondary outcomes (e.g., 0.35 standard deviation units difference in ODI across arms) are also detectable with at least 80% power under similar assumptions. Additionally, we plan to conduct secondary longitudinal analyses involving multiple time points per participant (i.e., more data observations) using likelihood-based methods that are robust to missing data. Therefore, we anticipate adequate power to evaluate differences across arms in outcome trajectories. **Since our target final analytic sample size is 224 total participants, if we can reach our target with fewer participants enrolled than 360, we will consider stopping enrollment.** We will plan to monitor dropout rates, ICC, standard deviation, and within-participant correlation

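### Age is tested as a moderator only through a cut at 65, which discards information if the effect changes gradually with age; a pre-specified continuous-age test is a cheap improvement to this exploratory analysis

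*SAP*

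**What the plan says.** In section 6 of the SAP, under Exploratory Analyses, the stated purpose is: "we will conduct exploratory analyses to study effects among subgroups of patients (moderator analyses". The third moderator is given as "Age ≥ 65 years old" and nothing more. Each moderator model contains the baseline outcome, "treatment assignment, a moderator variable, and a treatment-moderator interaction". One model is fitted per outcome and moderator, for PROMIS-PI, ODI and opioid use at three months. On inference the SAP says: "Tests for the treatment-moderator interaction will be two-sided with a 5% type I error rate, and we will report point estimates and 95% confidence intervals".

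No continuous or spline form of the age interaction is planned. Elsewhere age appears without a cut: section 3 lists it among the adjustment covariates, and the primary model in section 6 includes "known influential predictor effects (age, sex, Keele STarT score"). Section 3 allows further effect modifiers, but that clause concerns the other variables listed there, and such analyses would be labelled post hoc.

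The SAP gives neither the expected age distribution nor the number of patients aged 65 or over.

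**The concern.** A single cut treats patients aged 20 and 64 as alike and patients aged 64 and 66 as different. If the benefit of the intervention rises or falls steadily with age, a two-level variable captures only part of that trend. The precision of the interaction is also governed by the smaller of the two age groups.

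What is at stake is the reading of an exploratory result. A non-significant interaction could be taken to mean that the effect does not depend on age, when the test could reliably detect only a large difference between the two age groups. Nothing in the primary or secondary analyses depends on this.

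**Working it through.** **Inputs from the SAP (section 8).** 224 analysed patients, 112 per arm; SD 10; baseline to follow-up correlation 0.50; target difference 3.5 points; ICC 0.10; two-sided 5%. Residual SD after baseline adjustment = 10 × √(1 − 0.50²) = 8.66.

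**Input not in the SAP.** The share p of patients aged 65 or over, taken as 10-25%, with 50% added as the best case for any cut.

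**Step 1: reproduce the plan's own power.** The SAP states that "a final sample size of 16 physicians per arm and 7 participants per physician (n=224 total or 112 per arm) achieves 84% power" for the target difference under the inputs just listed. With 16 physicians per arm, 7 patients each and cluster autocorrelation 1:
- Design effect = 1 + 6 × 0.10 = 1.6.
- R = (7 × 0.10 + 0.90 × 0.50)/1.6 = 0.719, so 1 − R² = 0.483.
- SE = √(2 × 100/112 × 1.6 × 0.483) = 1.175.
- Power = Φ(3.5/1.175 − 1.96) = 84.6% (82.2% with a t reference on 30 df).

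The stated 84% is reproduced to within 2 points. It concerns the main effect; no power is stated for the age moderator.

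**Step 2: information kept by the cut.** If the effect is linear in age, the share kept is the squared correlation between age and the indicator. For normal age this is φ(z)²/[p(1 − p)], where z is the upper-p normal quantile. Where continuous age has 80% power, the cut has Φ(2.80 × √kept − 1.96).

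**Step 3: detectable interaction.** SE = 8.66 × √(2/n1 + 2/n0), with n1 = 112p and n0 = 112(1 − p); the difference detectable with 80% power is 2.80 × SE. Clustering is left out; the moderator model as described names no random physician effect. The 224 allows for 20% loss of both physicians and patients. With patient loss only, 360 × 0.80 = 288, and the detectable difference shrinks by √(224/288) = 0.882.

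| Assumed share 65+ | 65+ per arm (of 112) | Information kept | Power of cut where continuous has 80% | SE | Detectable, n=224 | Detectable, n=288 |
|---|---|---|---|---|---|---|
| 10% | 11.2 | 34% | 37% | 3.86 | 10.8 | 9.5 |
| 15% | 16.8 | 43% | 45% | 3.24 | 9.1 | 8.0 |
| 20% | 22.4 | 49% | 50% | 2.89 | 8.1 | 7.2 |
| 25% | 28.0 | 54% | 54% | 2.67 | 7.5 | 6.6 |
| 50% | 56.0 | 64% | 61% | 2.31 | 6.5 | 5.7 |

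So with normal ages the loss is 46-66% for a 10-25% share and never below 36%.

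**Step 4: other age distributions.** For uniform ages the share kept is 3p(1 − p). Ages spread evenly from 18 to 90 give p = 25/72 = 0.347 and 68% kept; from 18 to 75, p = 10/57 = 0.175 and 43-44% kept. Right-skewed (gamma) ages kept 23-66% across the shapes tried. The loss can therefore be as low as about a third.

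**Step 5: how continuous age performs.** The SE of the interaction per SD of age is 2 × 8.66/√224 = 1.157.
- Gradient of 1 point per SD: power Φ(1/1.157 − 1.96) = 14%.
- Gradient of 1.75 points per SD: 33%.
- 80% power needs 2.80 × 1.157 = 3.24 points per SD.

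**Step 6: simulation (4,000 trials, n=224).**

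| True shape | Ages | Continuous | Cut |
|---|---|---|---|
| Linear, 3.3 points per 16 years | Normal, 14.5% aged 65+ | 81% | 45% |
| Linear, 3.3 points per 16 years | Right-skewed, 12.3% aged 65+ | 84% | 57% |
| 9-point step at 65 | Normal | 42% | 76% |
| 9-point step at 65 | Right-skewed | 44% | 68% |

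**The case against.** The strongest reply is that the form of the moderator is a legitimate choice. The stated aim is to look at subgroups, a pre-specified 65-and-over group answers that directly, and a linear term answers a different question under an assumption of its own. If the effect steps at 65, the cut is the better test. This stands as far as it goes: the cut is not an error, and nothing in the SAP says which shape applies. Nor does the absence of a rationale for 65 carry weight, since that may sit in the protocol.

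Three stronger readings are tempting, and the document does not support them:

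- A reader might infer that the older subgroup is small and that half or more of the information is certainly lost. Both depend on an age distribution that the SAP does not give.
- A reader might blame the cut for the whole of the large detectable interaction. An ideal 50/50 moderator would already need about 6.5 points at 224, and 224 is the planned worst case for attrition.
- A reader might conclude that continuous age would find most plausible gradual effects that the cut misses. For small gradients it too would usually return a null result (Step 5). The confidence intervals already planned would show the imprecision under either form.

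What the objection does not remove is that, for a gradual effect, continuous age uses data already in hand more efficiently. Pre-specifying it guards against data-driven cuts just as well as pre-specifying 65 does.

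**Conclusion.** The point holds as a modest improvement to an exploratory analysis. The age-by-arm interaction is tested only through a cut at 65. If the effect is linear in age and ages are roughly normal, the cut loses at least 36% of the information, and 46-66% if 10-25% of patients are 65 or over; with skewed or uniform ages the loss can be about a third. The interaction detectable through the cut is about 7.5-10.8 PROMIS-PI points at 224 and 6.6-9.5 at 288, under the SAP's SD and correlation with clustering ignored. Part of that is the ordinary weakness of interaction tests. If the effect truly steps at 65, the cut loses nothing. The primary and secondary results are untouched.

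**What to change.** Amend the third moderator in section 6 before database lock, which the SAP anticipates on 7/25/25. Suggested content:

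- The moderator is age in years. The stated interaction test is arm-by-age, with the form fixed in advance: linear, or a restricted cubic spline with knots named, which spends extra degrees of freedom.
- Report the model-based arm difference (odds ratio for opioid use) with 95% CI at several ages, for example 35, 50, 65 and 75.
- Show the arm differences under 65 and at 65 or over with 95% CIs as a descriptive display.

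The cost is a short change of wording and one further model for each of the three outcomes, with no new data. Enrolment closed on 7/11/24, so the share aged 65 or over can be read from pooled baseline data without touching outcomes. The downside is that the linear test is weaker if the effect jumps at 65, which is why the 65-and-over estimate is kept. If the database is already locked, the continuous-age model should be added and labelled post hoc, as section 6 requires for departures from the plan.

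### Moderator analysis 4: approach 1 sets each NEED-PT treatment class against the undivided control arm, so its class terms mix effect with prognosis, and the interaction test cannot be estimated

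*SAP*

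**What the plan says.** Section 6 (Exploratory Analyses) lists four moderators. The fourth is the primary treatment classification, with five levels: "directional preference, traction, stabilization, manipulation, nociplastic presentation". The SAP acknowledges that "primary treatment classification is assigned only in those participants in the treatment arm (NEED-PT") and gives two approaches.

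- Approach 1: "we will modify GLMM to include treatment classification effects (as opposed to just a study arm effect").
- Approach 2: use matching methods to "match individuals in the NEED-PT arm who have a given primary treatment classification to control arm participants on baseline covariates", then fit a GLMM for each class separately. Propensity scores and augmented synthetic controls are given as examples, and neither is fixed.

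The same section then sets out the model for the moderator analyses. Besides the baseline outcome, its fixed effects are "treatment assignment, a moderator variable, and a treatment-moderator interaction". It adds "Separate models will be fit for each outcome and moderator" and "Tests for the treatment-moderator interaction will be two-sided with a 5% type I error rate". It makes no exception for the fourth moderator, and no adjustment for multiple comparisons.

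Section 3 names age, sex and the STarT score as covariates for the primary analyses. Length of pain and nature of injury are collected but are not planned covariates.

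**The concern.** A moderator analysis asks whether the treatment effect differs between types of patient, so each type must be identifiable in both arms. Here it is identifiable in one arm only. Approach 1 compares, for example, NEED-PT patients with a nociplastic presentation against all controls, most of whom may belong to other classes. Randomization does not protect that contrast. A class with a poor natural course would look unresponsive, and a class with a good course would look responsive, even if the effect were the same in all.

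The SAP does not rank the two approaches, attaches no caveat to approach 1, and does not say what happens if they disagree. The revision history gives the need to match controls to comparable classes as the reason for expanding this analysis. Approach 2 attempts that and approach 1 does not.

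**Working it through.** The plan gives no figure on this point to reproduce. The inputs from the SAP are the five classes, their absence in controls (Section 6), and 112 analysed participants per arm in 16 physician clusters of 7, SD 10, baseline-to-follow-up correlation 0.50 (Section 8). Class shares and class prognosis are not given and are assumed below.

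**Can the interaction be fitted?** Let T be treatment and C1 to C5 the class indicators, all zero in controls.

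| Model | Columns | Rank |
|---|---|---|
| Intercept, baseline, T, C1–C5, T×C1–T×C5 | 13 | 7 |
| Same with one class as reference (4 class and 4 product terms) | 11 | 7 |
| Intercept, baseline, T, C1–C5, no interaction | 8 | 7 |
| Approach 1: intercept, baseline, C1–C5 | 7 | 7 |

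The reason is exact: T = C1 + … + C5, and T×Ck = Ck for each class. If a few NEED-PT patients had no consultation and hence no class, the first equality would fail but the second would not, so the interaction would still be lost. Approach 1 itself can be fitted, but it contains no interaction.

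**What does an approach 1 coefficient estimate?** Let class k hold share p of patients, and let its untreated three-month mean, given the covariates, exceed that of the other classes by g. The control mean is p·μk + (1 − p)·μother, so

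bias = μk − [p·μk + (1 − p)·μother] = (1 − p) × g.

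Illustrations: 0.7 × 2 = 1.4; 0.8 × 3 = 2.4; 0.9 × 5 = 4.5 PROMIS-PI points. With g = 0 the bias is 0.

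**Simulation.** The setting was 2,000 trials per scenario, five equal classes, 112 per arm in clusters of 7, baseline correlation 0.5, an assumed ICC of 0.05 in the residual, and class indicators in an ANCOVA adjusted for the baseline outcome only, without a physician effect. Residual class prognosis was spread evenly from −s to +s.

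| s (assumed) | True effect | Mean class estimates, lowest to highest | Equality of classes rejected |
|---|---|---|---|
| 0 | 0 | −0.06 to 0.08 | 5% |
| 2 | 0 | −2.01 to 2.01 | 22% |
| 3.5 | 0 | −3.54 to 3.45 | 63% |
| 5 | 0 | −5.00 to 5.04 | 92.5% |
| 3.5 | −3.5 in every class | −7.04 to −0.05 | 62% |

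**Does a comparable-control analysis remove it?** A separate simulation used one class of about 20%, one baseline covariate predicting class and outcome, no true effect, 112 per arm, no clustering and 1,500 trials per scenario. It compared covariate-adjusted approach 1 with weighting controls to the class on the same covariate.

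| g | Bias, approach 1 | Bias, weighting |
|---|---|---|
| 0 | −0.05 | −0.06 |
| 2 | 1.41 | 1.34 |
| 3.5 | 2.63 | 2.46 |
| 5 | 3.76 | 3.54 |

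A further check at a 3.5-point gap agreed: 2.68 for approach 1 against 2.56 for weighting on the same covariates. When the weighting also used baseline variables that predict class and are absent from the approach 1 model, its bias fell to 0.06, against 2.33 for approach 1. The gain comes from the variables used, not from weighting as such.

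**The case against.** The SAP has seen the problem: it states that controls are unclassified and adds a matched analysis. Showing a simple and a matched contrast side by side is a normal exploratory strategy. The instructions specific to the fourth moderator can be read as replacing the general interaction model, in which case only an exempting sentence is missing. If the covariates of the main model carry over, STarT, a prognostic score, is already adjusted for. All of this stands, and it limits the weight of the point. It does not change what an approach 1 coefficient estimates, and the SAP does not state the exemption.

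A reader might infer three stronger things that the document does not support.

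- That approach 1 is biased by 1.4 to 4.5 points, around or above the 3.5-point lower bound of the minimum important difference. The SAP gives neither class shares nor class prognosis, and g may be zero.
- That the SAP declares the approach 1 terms to be class-specific treatment effects. It speaks of estimating impact only for the matched approach. The fault is the missing caveat and ranking.
- That one particular technique, such as weighting by the predicted probability of class, is needed in place of the planned matching. Both rest on measured baseline variables, and the choice is a preference.

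**Conclusion.** The point holds as a minor one. Two parts follow from the text and need no assumed figure. First, approach 1 can only contrast each class with the undivided control arm, so differences between its class terms are not evidence of effect modification unless class carries no prognosis beyond the covariates. Second, the interaction test stated for every moderator is not estimable for the fourth.

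The size of the bias is unknown; the simulated figures show only how it scales with an assumed residual spread. Approach 2 reduces it only as far as its matching variables explain class prognosis. The analysis is exploratory, and neither the primary nor the secondary between-arm estimates depend on it.

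**What to change.** Revise the text on the fourth moderator in Section 6:

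1. Present approach 1 as descriptive three-month outcomes by class within NEED-PT, with no effect claimed.
2. Make approach 2, with controls matched or weighted to each class, the only class-specific effect estimate, and fix the method.
3. Name the matching variables: baseline PROMIS-PI and ODI, STarT, age and sex, plus collected baseline variables likely to predict class and outcome, such as length of pain and nature of injury. Naming them matters because Section 3 would otherwise have analyses with additional covariates labelled post hoc.
4. Report balance for each class, and state the assumption that, given these variables, class is unrelated to the untreated outcome.
5. Exempt this moderator from the interaction model and its test.

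The cost is a few sentences and modest analyst time. The downside is wider intervals than the simple contrast gives, and residual bias wherever the assumption in item 4 fails.

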3. DEMOGRAPHICS AND BASELINE ASSESSMENTS

The following are specific demographic / baseline assessments of interest for analyses. **Primary analyses will adjust for these covariates as we anticipate they will influence outcome.** We plan to report both model-adjusted and simple unadjusted intervention effect estimates:

- 1) Sex
- 2) Age
- 3) Keele STarT Back Screening Tool: a nine-item survey which assesses risk for progression to chronic base pain

Additional demographics and clinical characteristics we plan to collect and summarize (i.e., we **do not plan to include as covariates in analyses**) include:

- 1) Race / ethnicity
- 2) Education level
- 3) Marital status
- 4) Employment status
- 5) Activity level at work for those that are working at baseline
- 6) Income level
- 7) Physical activity level according to self-report
- 8) Nature of injury
- 9) Length of pain at baseline
- 10) Primary diagnosis
- 11) Medications administered / prescribed during initial ED visit

Note that some additional exploratory analyses may examine these additional variables as covariates and/or effect modifiers as well. We will label any exploratory analyses involving additional potential covariates as post hoc in any dissemination materials.

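### Moderator analyses 1–3 leave out the physician clustering, so confidence intervals for arm effects within subgroups come out too narrow

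*SAP*

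**What the plan says.** For the moderator analyses, SAP section 6 (Exploratory Analyses) sets the outcome at month 3: "Analyses will focus on PROMIS-PI scores measured three months after patients’ index visits, as well as ODI scores and opioid use". The model class follows: "Analyses will involve generalized linear models with appropriate link functions (identity for PROMIS-PI and logit for opioid" use. The listed terms are those "that include fixed effects for baseline measures of the outcome of interest, treatment assignment, a moderator variable, and a treatment-moderator interaction", and "Separate models will be fit for each outcome and moderator". The opioid model is then called a logistic regression with Wald tests and intervals. The text gives no random physician effect, no time term, no age, sex or STarT adjustment, and no rule for a missing month-3 value.

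The primary model, earlier in section 6, is a repeated-measures linear mixed model. It has arm, baseline outcome, timepoint, timepoint-by-arm, age, sex and STarT as fixed effects, plus a random physician effect. Section 6 extends that strategy to additional outcomes, with generalized linear mixed models for binary and count outcomes.

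Moderator 4 (primary treatment classification) stands in the same list as moderators 1–3 but is given a mixed model: "First, we will modify GLMM to include treatment classification effects (as opposed to just a study arm effect"). The model class therefore changes within one subsection, and no reason is given.

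**The concern.** Section 1 states that physicians are the clusters and the units of randomization. Patients of one physician share an arm, so any comparison of arms, overall or inside a subgroup, carries between-physician variance. A model without a physician term treats patients as independent and reports too small a standard error for that comparison. The SAP promises point estimates and 95% confidence intervals for these analyses, and readers will look at the arm effect within each subgroup as well as at the interaction.

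There is a second, smaller effect. A single-visit model has no use for the Week 1, Month 1 and Month 2 answers of someone who missed month 3, whereas the primary model uses them.

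**Working it through.** **Inputs from SAP section 8.** Final sample of 16 physicians per arm with 7 participants each (n = 224); SD 10; difference 3.5; planning ICC 0.10; pilot ICC 0.01–0.04; baseline to follow-up correlation about 0.50; 20% loss of participants.

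**Step 1. The plan's own power figure.** The design effect is 1 + 6 × 0.10 = 1.6. The correlation of cluster means is r = (7 × 0.10 + 0.90 × 0.5)/1.6 = 0.719, assuming that the physician effect is the same at baseline and follow-up (the SAP does not say). Then SE = √[2 × 100 × 1.6 × (1 − 0.719²)/112] = 1.175, and power = Φ(3.5/1.175 − 1.96) = 84.6%, against 84% stated. The figure reproduces and this point does not touch it. It does show that the SAP treats clustering as real when it plans the trial.

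**Step 2. Overall arm effect with clustering ignored.** The standard error is too small by √[1 + (m − 1) × ICC]. The true size of a nominal 5% test is 2[1 − Φ(1.96/factor)]. With m = 7:

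| ICC | Design effect | SE understated by | True size |
|---|---|---|---|
| 0.01 | 1.06 | 1.03 | 5.7% |
| 0.04 | 1.24 | 1.11 | 7.8% |
| 0.10 | 1.60 | 1.26 | 12.1% |

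**Step 3. Arm effect in the reference stratum.** A subgroup has fewer patients per physician. If 30% have the moderator (assumed), the reference stratum has 0.7 × 7 = 4.9 per physician. The design effects are then 1 + 3.9 × ICC = 1.039, 1.156 and 1.39, and the true sizes 5.4%, 6.8% and 9.6%. As the moderator becomes rarer, these move towards the values in step 2. Simulation of the listed model (ordinary least squares with baseline, arm, moderator and interaction; 40 physicians × 7; 30% moderator) agrees: 7.4% at ICC 0.04 and about 10% at 0.10. With the physician effect restored it gives 4–5%. Overall, this is about 6%, 7–8% and 10–12%.

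**Step 4. Interaction test.** In the same simulation its rejection rate under the null is 5.0% at ICC 0.04 and at ICC 0.10, because the shared physician effect largely cancels between strata. It rises to about 6.7–6.8% only if the moderator's effect also varies between physicians (assumed slope variance 0.05–0.10). The empirical SD of the interaction estimate at ICC 0.10 is 0.223 without the physician effect and 0.219 with it, so precision hardly changes.

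**Step 5. Cost of using month 3 alone.** Let R² be the share of month-3 variance explained by Week 1, Month 1 and Month 2 after baseline adjustment. With exchangeable correlation ρ across all visits (assumed 0.5, 0.65, 0.75), the correlation given baseline is p = ρ/(1 + ρ) = 0.333, 0.394, 0.429. Then R² = 3p²/(1 + 2p) = 0.200, 0.260, 0.297.
- If all 20% missing at month 3 answered the three earlier visits, the variance ratio of mixed model to single-visit model is 1 − 0.2R² = 0.960, 0.948, 0.941, a gain of 4–6%.
- If half of them have no follow-up at all, it is (1 − R²) + R² × 0.8/0.9 = 1 − R²/9 = 0.978, 0.971, 0.967, a gain of 2–3%.

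These ratios are for a month-3 mean and are only indicative for the interaction contrast.

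**Step 6. Which ICC applies.** Steps 2 and 3 need the ICC left after baseline adjustment. If the raw ICC is 0.10 and the physician effect is unchanged from baseline, as in step 1, the patient-level correlation is 0.10 + 0.90 × 0.5 = 0.55. The residual ICC is then 0.10 × 0.45²/(1 − 0.55²) = 0.029. If the two physician effects are unrelated, the correlation is 0.45 and the residual ICC is 0.10 × (1 + 0.45²)/(1 − 0.45²) = 0.15. The table should be read across its range.

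**The case against.** The strongest reply is that the sentence lists fixed effects only, and that moderator 4's wording presupposes a mixed model as the base, so a physician effect may be intended throughout. That is possible. But the text names generalized linear models and a logistic regression for the general case and a mixed model for moderator 4 alone. An analyst following it would fit no physician effect, and at the least the subsection needs reconciling.

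It is also fair that these are exploratory tests without multiplicity control, that pilot ICCs were small, and that the interaction test, the formal test of moderation, is nearly unaffected. All of that stands and limits the importance of the point.

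Several stronger readings are tempting, and the SAP does not support them:
- A reader might infer that dropping the physician effect loses precision. Step 4 shows almost no loss; the harm is to the stated uncertainty of arm effects.
- A reader might see a broken commitment on age, sex and STarT. Section 3 says "Primary analyses will adjust for these covariates as we anticipate they will influence outcome", and that covers primary analyses only. Age and STarT also enter through moderators 3 and 2, and any precision gain from full adjustment has to be assumed.
- A reader might say that the SAP prescribes complete cases. It does not. That follows from a single-visit model with no imputation stated, since the multiple imputation and weighting in section 7 are described for the mITT and ITT analyses. Nor does it follow that subgroup effects must disagree with the overall effect. A baseline-adjusted complete-case analysis remains valid if missingness depends only on arm, baseline outcome and moderator.
- A reader might object to the cut-points. Moderator 2 is a composite of "baseline measures of PROMIS pain scores are ≥ 60" or a high-risk STarT subscore, so a continuous PROMIS-PI term would answer a different question. Keeping the planned cut-points is a legitimate choice.

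**Conclusion.** The point holds for moderators 1–3 and is minor. As written, these analyses ignore the unit of randomization, and arm effects within subgroups get intervals that are too narrow: slightly at ICC 0.01, and by roughly a fifth to a quarter in standard error at ICC 0.10 (factor √1.39 = 1.18 for a stratum of 4.9 per physician, 1.26 for all 7). The sizes assume 7 participants per physician, equal clusters, and SAP ICC values that apply after baseline adjustment. The test of interaction is sound unless moderator effects differ between physicians. The loss from using month 3 alone is modest and rests on assumed correlations and on how many of the missing answered earlier visits. The primary analysis, the 84% power figure and moderator 4 are not affected.

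**What to change.** For moderators 1–3, replace the single-visit generalized linear model with the mixed model already specified in section 6. Keep the random physician effect, baseline outcome, age, sex and STarT, and add moderator, arm-by-moderator and arm-by-moderator-by-time terms (with moderator-by-time, so that the hierarchy is complete). Test the month-3 arm-by-moderator contrast, and report the month-3 arm effect in each stratum from the same fit. Keep the planned cut-points.

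For opioid use, section 6 anticipates unstable binary models and would then drop the physician effect in favour of a participant effect. That fallback would bring the problem back. State instead that, if the repeated-measures model does not converge, a month-3 model with a physician random effect or physician-clustered standard errors will be used, and say how missing month-3 values are handled.

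The primary model is reused, so little new work is needed. The price is more parameters and possible convergence trouble for the binary outcome. SAP version 2.0 predates the planned database lock, and section 9 provides for documented updates.
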